* Correction of preoperative anemia or hemodilution only; the number of PRBCs used should only be considered in the UDPB when accompanied by other signs of perioperative bleeding. Prophylactic/preoperative transfusion of blood products and factor concentrates do not contribute to UDPB.

Exact measurement of postoperative blood loss is difficult, given that laboratory values such as hemoglobin and hematocrit are heavily influenced by intra- and postoperative fluid shifts, and transfusion protocols may vary by institution. However, chest tube drainage (CTD) in the early postoperative period (≤ 24 hours) is a metric that is easily quantifiable and routinely used in clinical practice. Enhanced Recovery After Surgery (ERAS) guidelines in cardiac surgery recommend chest tube placement and drainage to prevent accumulation of blood in the chest and mediastinum during the postoperative period, and their placement is standard of care following open cardiac surgery. [37]

The inclusion of CTD in the composite primary effectiveness endpoint is underscored by its clinical relevance evidenced by the use of CTD in everyday clinical practice protocols for postoperative decision-making (e.g., criteria for surgical re-exploration) that rely on rate and volume of chest tube drainage. [38] While postoperative CTD volume during the first 12 hours is already included within the UDPB classification, volume of 24-hr CTD has been identified as an important independent metric. The 24-hr CTD volume has been demonstrated to correlate with other important clinical outcomes, including transfusion requirements and duration of hospital stay in linear regression models. [39, 40] Excessive 24-hr CTD as defined by $>1000\text{mL}$ has been shown to be an independent predictor of postoperative acute kidney injury (odds ratio 1.40, $p < 0.001$). [41] Most importantly, 24-hr CTD is an independent predictor of in-hospital mortality with a linear, **dose-dependent** relationship that is independent of blood transfusion requirement. [23]

Key Secondary Endpoints: Evaluation of the change in preoperative to postoperative apixaban and rivaroxaban drug concentrations will be the key secondary endpoints. These drug removal endpoints will quantify the extent of DrugSorb-ATR's apixaban and rivaroxaban removal capabilities, while also providing a mechanistic relationship to the improved surgical and post-surgical bleeding outcomes (i.e., less drug = less bleeding).

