11. STATISTICAL CONSIDERATIONS

General statistical considerations: descriptive summaries will be presented using mean with standard deviation (SD), median, minimum and maximum for continuous variables and as count and percent of subjects for categorical variables. Inferential statistical tests will be two-sided and use alpha (α) of 0.05 as a critical value, unless noted otherwise. Statistical analysis will be carried out using SAS Version 9.4 or later and/or R software language.

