Approximately 120 combined DOAC subjects meeting the study inclusion criteria ([Section 4.4.1](#)) will be randomized in a 1:1 ratio to the treatment and control arms. A combined DOAC population is planned for analysis in the current study since apixaban and rivaroxaban share the same mechanism of action, same indications for use, same risk for post-surgical bleeding outcomes, have been shown in *ex vivo* testing to have nearly identical removal rates when treated with the study device, and are therefore considered exchangeable.

In terms of the composite primary effectiveness bleeding endpoint, while bleeding is known to be of significant risk in patients on both apixaban and rivaroxaban undergoing CT surgery without preoperative washout, literature quantifying postoperative bleeding outcomes is limited in this specific population. However, published real-world use experience from the Asklepios Klinik St. Georg research group (Hamburg, Germany) has demonstrated highly similar treatment effects for intraoperative CytoSorb® removal of ticagrelor and rivaroxaban in patients undergoing emergent CT surgery. [12] The difference between treatment and control groups regarding postoperative blood loss (in the form of 24hr chest tube drainage volume), reoperation rates for bleeding, and transfusion volumes were comparable between the ticagrelor and rivaroxaban cohorts. Thus, for the purpose of this study, we will anticipate the same treatment effects for DrugSorb-ATR therapy in subjects

undergoing CT surgery (within 36 hours of last DOAC dose) as were utilized for the STAR-T trial (which enrolled subjects undergoing CT surgery within 48 hours of last ticagrelor dose). The difference in timing between last drug dose and start of surgery for the DOAC vs. ticagrelor studies is necessary due to the difference in recommended washout periods between the DOACs and ticagrelor.

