Because of exchangeability between apixaban and rivaroxaban, the anticipated proportions of individual DOACs expected in the trial (ranging from 40% - 60%, reflective of real-world use patterns), are not assumed to impact power or sample size. Assuming a 5% dropout rate, a total of 114 subjects (57 per arm) are expected to be evaluable for effectiveness and safety. Sample size is based on published response rates for the primary effectiveness Win Ratio sub-components, as noted for rivaroxaban and ticagrelor (above) with a bridge to apixaban, and can be calculated via an iterative simulation process with programming code available in an appendix to Redfors et al. (2019). [16] As a sensitivity exercise, power was estimated under varying conditions where the ratios of apixaban to rivaroxaban subjects were allowed to range from 40% to 60%, for either drug, and under assumptions of +/-5% worse vs. better outcomes for apixaban as compared to rivaroxaban (see **Table 3**). Power for the study to reject a false null hypothesis is formally estimated where apixaban is assumed equally comparable to rivaroxaban, at a subject ratio of 50:50 (see **bold** results in **Table 3**, below).

Table 3. Win Ratio Effect Size Assumptions with Power and Sample Size Estimates Under Varying Conditions

A:R* Com- para- bility	Ratio A:R	n Per Group	Effect Size						Power	
			Component #1		Component #2		Component #3			
			Fatal Bleeding	UDPB (Class ≥2)	Treatment Event	Control Event	Treatment Event	Control Event		
A Has 5% Higher Event Rate Than R Among Treated Subjects	40:60	Interim Analysis N=39	3.06%	3.00%	24.79%	40.50%	489.6 (253)	800 (253)	88.1%	
	40:60	End of study N=56	3.06%	3.00%	24.79%	40.50%	489.6 (253)	800 (253)	99.3%	
	50:50	Interim Analysis N=39	3.07%	3.00%	24.91%	40.50%	492.0 (253)	800 (253)	87.1%	
	50:50	End of study N=56	3.07%	3.00%	24.91%	40.50%	492.0 (253)	800 (253)	99.2%	
	60:40	Interim Analysis N=39	3.09%	3.00%	25.03%	40.50%	494.4 (253)	800 (253)	86.0%	
	60:40	End of study N=56	3.09%	3.00%	25.03%	40.50%	494.4 (253)	800 (253)	99.2%	
A = R Event Rate Among Treated Subjects	40:60	Interim Analysis N=39	3.00%	3.00%	24.30%	40.50%	480 (253)	800 (253)	91.3%	
	40:60	End of study N=56	3.00%	3.00%	24.30%	40.50%	480 (253)	800 (253)	99.5%	
	50:50	Interim Analysis N=39	3.00%	3.00%	24.30%	40.50%	480 (253)	800 (253)	91.3%	
	50:50	End of study N=56	3.00%	3.00%	24.30%	40.50%	480 (253)	800 (253)	99.5%	
	60:40	Interim Analysis N=39	3.00%	3.00%	24.30%	40.50%	480 (253)	800 (253)	91.3%	

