Benchtop studies of drug removal by DrugSorb-ATR (data on file, CytoSorbents Corporation) demonstrate concentration and time dependent absolute drug removal, which are nearly identical for both apixaban and rivaroxaban. Based on these benchtop studies, a conservative estimate of 40% reduction in blood concentration of DOAC between pre- and post- DrugSorb-ATR removal is expected, with a standard deviation of 40%, in the treatment arm. Minimal change is expected in the control arm. A two-sample t-test will be used to evaluate the difference between treatment arms. Due to highly variable baseline drug levels in the study population, percent change from baseline will be analyzed as opposed to observed values.

Additional secondary endpoints include 24-hour CTD (volume [mL]), total platelet transfusions during the index hospitalization (volume [mL] and units), and total PRBC transfusions during the index hospitalization (volume [mL] and units). Twenty-four-hour CTD (mL) will be assessed via two-sample t-test for mean difference. In the event the assumptions for a two-sample t-test are not met, a nonparametric test such as a Mann-Whitney test will be employed, with median and range values provided in the output. An additional analysis of 24-hour CTD will compare the frequency of subjects falling into volume categories (i.e., <500 mL, 500 to <750 mL, 750 to <1000 mL, 1000 to <1250 mL, 1250 to <1500 mL, and ≥ 1500 mL), and will use a Fisher-Freeman-Halton exact test to compare treatment groups. The transfusion endpoints will all be analyzed using two-sample t-tests for mean differences, and Fisher-Freeman-Halton exact tests for units. In the event the assumptions for a two-sample t-test are not met, a nonparametric test such as a Mann-Whitney test will be employed, with

median and range values provided in the output. The remaining Win Ratio component parts will also be included as secondary endpoints: proportions of fatal perioperative bleeding events will be assessed via Fisher's exact test; and proportions of UDPB events (by category) will be assessed via a Fisher-Freeman-Halton exact test. All surgical re-exploration for excessive bleeding, including those events occurring beyond the timeframe captured within the UDPB component of the primary endpoint will be captured as a secondary endpoint. Time to re-exploration will be considered.

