11.4. Subgroup Analysis

Results comparing the two treatment arms based on the components of primary effectiveness endpoints will be contrasted across clinically meaningful subgroups according to the following factors:

- DOAC type (apixaban vs. rivaroxaban),
- Planned surgery type (CABG-alone vs. all other types of CT surgery)
- EuroScore II score (<7% vs. $\geq 7\%$),
- STS Risk score (<4% [low], 4-8% [intermediate], $\geq 8\%$ [high]),
- Left ventricular ejection fraction (LVEF) [$\geq 50\%$ (normal), 40-49% (mild dysfunction), 30-39% (moderate dysfunction), <30% (severe dysfunction)]
- Baseline thrombocytopenia (platelet count <150,000 μL vs. $\geq 150,000 \mu\text{L}$),
- Age group (<65 vs ≥ 65 years old),
- Biologic sex (F vs. M),
- History of MI (Y vs. N), and
- History of stroke (Y vs. N).

For the fatal bleeding events occurring within 48hrs post-index operation, and moderate, severe, or massive bleeding events components, a logistic regression will be utilized with treatment, group and their interaction included in the model. Details will be provided in the SAP.

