Appendix 2: Clinical Laboratory Evaluations

Clinical chemistry:	Hematology:
Alanine aminotransferase ^a Albumin ^a Alkaline phosphatase ^a Aspartate aminotransferase ^a Blood urea nitrogen Calcium Ionized Calcium ^a Chloride Creatinine Direct bilirubin ^a Gamma-glutamyl transferase ^a Glucose Potassium Sodium Total bilirubin ^a Total protein ^a	Hematocrit Hemoglobin Platelet count Red blood cell count White blood cell (WBC) count Differential ^a
Coagulation tests:	Other, including cardiac biomarkers
Coagulation Panel: Activated partial thromboplastin time International normalized ratio Prothrombin time Fibrinogen ^a Point of Care Test(s): Activated clotting time (ACT) [refer to Schedule of Assessments for specific timing of sampling]	Serum pregnancy test ^b Cardiac troponin (cTn) ^c

^a Performed only if part of routine standard of care. Sponsor agrees to forego the data if the assessments are not performed and recorded^b Performed in serum at Screening for all females of childbearing potential. Pre-consent test results done during the current admission MAY be used. Pre-consent test results done before the current admission MAY NOT be used.^c Performed in serum Screening for all females of child-bearing potential. Post-op testing will be per institutional standard of care, or as indicated by symptoms and concern for perioperative myocardial infarction

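### Adjusting the two alpha-controlled transfusion comparisons for baseline hemoglobin or platelet count and for surgery type would gain a little power at almost no cost; the unadjusted tests are valid

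*Combined protocol and SAP*

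**What the plan says.** **Test.** For platelet and PRBC transfusions, Section 11.3 states: "The transfusion endpoints will all be analyzed using two-sample t-tests for mean differences". The same sentence adds Fisher-Freeman-Halton exact tests for units, and the next gives a Mann-Whitney fallback if the t-test assumptions fail. No covariate is named, and no adjusted analysis of these endpoints appears elsewhere.

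**Role.** Section 11.3 places platelet and then PRBC transfusions fifth and sixth, the last steps of the step-down sequence. Section 11 sets the level: "Inferential statistical tests will be two-sided and use alpha (α) of 0.05 as a critical value".

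**Measure.** Section 11.1 states the hypotheses and the power in units. The Synopsis attaches the same power figures, 98.0% and 96.7%, to volume in mL.

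**Baseline data.** Appendix 2 lists "Hematocrit Hemoglobin Platelet count Red blood cell count White blood cell (WBC) count" under hematology, and hemoglobin and platelet count carry no flag limiting them to routine care. Table 6 schedules hematology for every subject at Screening, and its footnotes allow pre-consent values if needed. Planned surgery (CABG alone or other) is a stratification factor in Section 6.1.

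**Relevance in the plan's own words.** The Table 1 footnote in Section 3 reads "Correction of preoperative anemia or hemodilution only; the number of PRBCs used should only be considered in the UDPB", and goes on to require other signs of bleeding. Section 11.4 lists "Baseline thrombocytopenia (platelet count <150,000" among the subgroup factors for the primary-endpoint components.

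**The concern.** Subjects who start with low hemoglobin or a low platelet count may be transfused more whatever their arm. That variation sits in the error term of an unadjusted comparison. The UDPB footnote limits the effect of anemia-driven PRBC units on the bleeding class, but the PRBC secondary endpoint counts all units in the index hospitalization without such a limit. Surgery type is used in randomization because bleeding risk differs by procedure, yet it is left out of these tests. Where a stratification factor is prognostic, an analysis that ignores it has a larger standard error than it needs.

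At stake is precision on two endpoints that can carry a claim, mainly if the trial stops at the interim or the true effects are smaller than assumed.

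**Working it through.** **Inputs.** Section 11.1 gives 120 subjects who "will be randomized in a 1:1 ratio to the treatment and control arms". "Assuming a 5% dropout rate", 120 × 0.95 = 114, and "a total of 114 subjects (57 per arm) are expected to be evaluable for effectiveness and safety". Platelets: 0.32 (SD 0.9) vs 1.6 (SD 2.2) units, difference 1.28, a reduction of 1.28/1.6 = 80%. PRBC: 1.3 (SD 2.1) vs 4.4 (SD 5.7) units, difference 3.1, a reduction of 3.1/4.4 = about 70%. Two-sided alpha is 0.05. The interim sample is 40 per arm (Section 11.6).

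**Step 1: reproduce the plan.** For the unequal-variance t-test, SE = √[(s₁² + s₂²)/n], with Satterthwaite degrees of freedom and the noncentral t.

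- Platelets, n = 57: SE = √[(0.81 + 4.84)/57] = 0.315; 1.28/0.315 = 4.07; power 98.0% (stated 98.0%).
- PRBC, n = 57: SE = √[(4.41 + 32.49)/57] = 0.805; 3.1/0.805 = 3.85; power 96.7% (stated 96.7%).
- At n = 40 the same formula gives 91.6% and 88.6%.

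**Step 2: adjust, normal-theory formula.** If the covariate has within-arm correlation ρ with the outcome, both SDs are multiplied by √(1 − ρ²). The documents give no ρ. The range 0.3 to 0.5 is an assumption (variance cut of 9% to 25%).

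| Case | Unadjusted | ρ = 0.3 | ρ = 0.5 | Gain (points) |
|---|---|---|---|---|
| Platelets, 57 per arm | 98.0% | 98.8% | 99.6% | 0.8 to 1.6 |
| PRBC, 57 per arm | 96.7% | 97.8% | 99.2% | 1.1 to 2.5 |
| Platelets, 40 per arm | 91.6% | 93.9% | 97.1% | 2.3 to 5.5 |
| PRBC, 40 per arm | 88.6% | 91.3% | 95.5% | 2.7 to 6.9 |

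**Step 3: allow for skewed counts.** The SDs exceed the means, so the formula is only a guide. Negative-binomial counts were simulated to match the stated means and SDs, with a normal covariate linked at latent correlation 0.3 or 0.5. The unadjusted Welch test was compared with a linear model using HC3 standard errors.

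- 40 per arm, covariate slope allowed to differ by arm (3,000 trials): PRBC 95.1% to 96.6% (ρ 0.3) and 94.4% to 98.3% (ρ 0.5); platelets 95.5% to 96.3% and 96.0% to 98.6%. The gains are 0.8 to 3.9 points.
- 40 per arm, common slope (4,000 trials): gains of 0.3 to 2.2 points.
- 57 per arm, either model: 1 point or less, from about 99%.
- Type I error of the HC3 model was 4.1% to 4.9% in one set of runs and 3.7% to 4.8% in the common-slope runs.

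The simulated gains are smaller for two reasons. The unadjusted test already has more power with these counts than the formula gives. The same nominal ρ also explains less variance on the count scale: within-arm R² at 57 per arm was about 0.06 at ρ 0.3 and 0.14 to 0.16 at ρ 0.5.

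**Step 4: robustness case.** Section 11.1 discounts the chest-tube drainage and UDPB effects to about a 40% reduction but states no discount for transfusions. With a 40% reduction (0.64 and 1.76 units), the stated SDs and 57 per arm, the formula gives PRBC 57.8% unadjusted and 61.9% to 70.2% adjusted, and platelets 51.9% and 55.7% to 63.9%.

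**The case against.** The strongest reply is that nothing needs repair. A t-test after stratified randomization is valid, its standard error already allows for chance baseline imbalance, and on the plan's inputs it has about 97% to 98% power. All of that stands.

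Three further objections also stand:

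- **The correlation is unknown.** The UDPB footnote is a scoring rule, and the platelet subgroup concerns the primary components. Neither shows how strongly baseline values predict transfusion here. A correlation of 0.5 is demanding for platelets, since a negative binomial matched to 0.32 (SD 0.9) puts about 82% of treated subjects at zero.
- **Forty per arm is a floor.** Table 3 puts interim power at 91.3% in its base case, so an early stop is likely on the plan's assumptions. But Section 11.6 keeps enrolling during the interim analysis and adds those subjects to the final analysis.
- **Section 11 is a summary.** Section 9 says the analyses will be detailed in the SAP. Section 11.3, however, does not itself defer these tests.

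A reader might infer from the formula that adjustment is worth 5 to 7 points at the interim. That is its upper end at ρ = 0.5, and the count-based simulation does not bear it out. A reader might also take the 40% case as a shortfall in the stated power. It is not: the plan states its transfusion effects and the power follows from them. The case tests sensitivity to smaller effects, and adjustment would not restore high power there.

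None of this shows that adjustment does harm.

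**Conclusion.** The point holds as an efficiency improvement, worth considering rather than required. Both endpoints are alpha-controlled, their tests use no covariate, and the relevant baseline values are already required. The documents do not support calling the unadjusted test an error or the endpoints underpowered.

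At the planned effects and an assumed ρ of 0.3 to 0.5, the gain is 1 point or less at 57 per arm and about 1 to 4 points at 40 per arm in count-matched simulation, with a common-slope model towards or below the low end. The normal-theory formula gives about 1 to 2.5 and 2 to 7 points. These figures rest on the stated means and SDs, alpha of 0.05 for these steps at either sample size, and a correlation that the documents do not supply. Any contribution from surgery type was not quantified.

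A separate weakness should be settled in the same edit: the plan does not say whether units or volume, or which of the named tests, carries the confirmatory decision.

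**What to change.** Amend Section 11.3 and the SAP before any unblinding, including the interim:

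1. Name units as the single confirmatory measure for each transfusion endpoint, as in the hypotheses and power statements of Section 11.1, and align the Synopsis.
2. Make the confirmatory test a linear model for units on treatment, planned surgery type, and baseline hemoglobin (PRBC) or baseline platelet count (platelets). Use HC3 standard errors, because the assumed SDs differ more than twofold between arms. Report the adjusted mean difference with its confidence interval. If a centred treatment-by-covariate term is wanted, specify it now.
3. Keep the unadjusted t-test, Mann-Whitney and Fisher-Freeman-Halton tests as sensitivity analyses.
4. State a simple rule for missing baseline values, such as mean imputation.

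The cost is wording, a slightly more complex model and the missing-value rule. No extra subjects or measurements are needed.

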11.4. Subgroup Analysis

Results comparing the two treatment arms based on the components of primary effectiveness endpoints will be contrasted across clinically meaningful subgroups according to the following factors:

- DOAC type (apixaban vs. rivaroxaban),
- Planned surgery type (CABG-alone vs. all other types of CT surgery)
- EuroScore II score (<7% vs. $\geq 7\%$),
- STS Risk score (<4% [low], 4-8% [intermediate], $\geq 8\%$ [high]),
- Left ventricular ejection fraction (LVEF) [$\geq 50\%$ (normal), 40-49% (mild dysfunction), 30-39% (moderate dysfunction), <30% (severe dysfunction)]
- Baseline thrombocytopenia (platelet count <150,000 μL vs. $\geq 150,000 \mu\text{L}$),
- Age group (<65 vs ≥ 65 years old),
- Biologic sex (F vs. M),
- History of MI (Y vs. N), and
- History of stroke (Y vs. N).

For the fatal bleeding events occurring within 48hrs post-index operation, and moderate, severe, or massive bleeding events components, a logistic regression will be utilized with treatment, group and their interaction included in the model. Details will be provided in the SAP.

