	60:40	End of study N=56	3.00%	3.00%	24.30%	40.50%	480 (253)	800 (253)	99.5%	
A Has 5% Lower Event Rate Than R Among Treated Subjects	40:60	Interim Analysis N=39	2.94%	3.00%	23.81%	40.50%	470.4 (253)	800 (253)	93.6%	
	40:60	End of study N=56	2.94%	3.00%	23.81%	40.50%	470.4 (253)	800 (253)	99.7%	
	50:50	Interim Analysis N=39	2.93%	3.00%	23.69%	40.50%	468.0 (253)	800 (253)	94.2%	
	50:50	End of study N=56	2.93%	3.00%	23.69%	40.50%	468.0 (253)	800 (253)	99.7%	
	60:40	Interim Analysis N=39	2.91%	3.00%	23.57%	40.50%	456.6 (253)	800 (253)	94.7%	
	60:40	End of study N=56	2.91%	3.00%	23.57%	40.50%	456.6 (253)	800 (253)	99.8%	

* A, R = apixaban, rivaroxaban.

Notes: n = number; UDPB = Universal Definition of Perioperative Bleeding; CTD = chest tube drainage (volume [mL]).

Component #1 minimum rates of 3.0% assumed as a conservative approach.

Component #2 rates based on Russo et al. (2019), however, with a discount applied to bring the Treatment arm up to ~40% reduction on the Control arm. [42]

Component #3 rates based on Hassan et al. (2019), however, with a discount applied to bring the Treatment arm up to ~40% reduction on the Control arm. [12]

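### At the planned 3% rate the Section 11.4 interaction model for 48-hour fatal bleeding will usually have no finite estimate, and no win ratio by DOAC type is specified

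*Combined protocol and SAP*

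**What the plan says.** Section 11.4 lists ten factors: eight with two levels, the STS risk score with three and LVEF with four. It states what will be compared: "Results comparing the two treatment arms based on the components of primary effectiveness endpoints will be contrasted across clinically meaningful subgroups". It then names one model for two outcomes, 48-hour fatal bleeding and UDPB class 2 or higher: "a logistic regression will be utilized with treatment, group and their interaction included in the model". It gives no rule for sparse or empty cells, no subgroup method for 24-hour chest tube drainage (CTD), and no win ratio within subgroups. Further detail is left to a SAP that is not part of the text supplied.

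The planning figures are in Section 11.1. Table 3's base case has fatal bleeding at 3.00% in both arms, with the note "Component #1 minimum rates of 3.0% assumed as a conservative approach". UDPB class 2 or higher is 24.30% on treatment against 40.50% on control. On sample size, "a total of 114 subjects (57 per arm) are expected to be evaluable for effectiveness and safety".

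Three other places bear on the point. Section 6.1 stratifies randomisation by DOAC type, and Section 6.2 keeps each drug between 40% and 60% of the sample. Section 11.3 pools the two drugs for the primary win ratio and uses Fisher's exact test for the overall comparison of fatal bleeding. The Synopsis announces subgroup analyses of efficacy, including by DOAC type, but names neither outcome nor method.

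**The concern.** A logistic model with treatment, subgroup and their interaction is saturated: it has one parameter for each treatment-by-subgroup cell. Fitted by maximum likelihood, its estimates are all finite only if every cell contains at least one subject with the event and one without. With about three fatal bleeds in the whole trial, some cell will usually have none. Software then reports a very large coefficient with a meaningless standard error, or fails to converge. The plan uses an exact test for the overall fatal-bleeding comparison, yet names a large-sample model for the sparser subgroup comparison.

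The second part is a gap. The primary result is a single win ratio over apixaban and rivaroxaban together. A reader will ask whether it looks similar for each drug, and Section 11.4 specifies no estimate on that scale. At stake are the usefulness of an exploratory table and the description of consistency between drugs. The primary test is not affected.

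**Working it through.** **Inputs.** Fatal-bleeding rate 3.0% per arm, UDPB class 2 or higher 24.3% against 40.5%, CTD 480 against 800 mL with SD 253 (Section 11.1 and Table 3); 114 evaluable, 57 per arm (Section 11.1); DOAC shares 40% to 60% (Section 6.2). The documents give no shares for the other factors, so splits from 50:50 to 10:90, and equal levels for STS and LVEF, are assumptions.

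**Reproducing the plan's figure.** A simulation of the Finkelstein-Schoenfeld test on the Table 3 base case (4,000 trials, independent components, normal CTD) gave 99.5% power at 56 per arm with a critical Z of 2.00, and 91.5% at 39 per arm with Z of 2.44. Table 3 states 99.5% and 91.3%, so the inputs have been read as the plan intends.

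**Expected events.** 0.03 × 114 = 3.42, or 1.71 per arm. The binomial probability of three or fewer is 55%; in those trials four cells cannot all contain an event. The probability that at least one arm has no fatal bleed is 1 − (1 − 0.97^57)² = 1 − (1 − 0.176)² = 32%.

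**Chance that every cell has an event.** This is the product over cells of 1 − 0.97^n, where n is the cell size.

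| Factor | Cell sizes | All cells have an event | At least one empty |
|---|---|---|---|
| Two levels, 50:50 | 4 × 28.5 | (1 − 0.97^28.5)^4 = 11.3% | 89% |
| Two levels, 40:60 (limit for DOAC type) | 2 × 22.8, 2 × 34.2 | 10.5% | 90% |
| Two levels, 30:70 | 2 × 17.1, 2 × 39.9 | 8.2% | 92% |
| Two levels, 10:90 | 2 × 5.7, 2 × 51.3 | 1.6% | 98% |
| STS, three equal levels | 6 × 19 | 0.7% | 99.3% |
| LVEF, four equal levels | 8 × 14.25 | 0.02% | over 99.9% |

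For STS and LVEF, an empty cell means that at least one interaction coefficient has no finite estimate.

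**What a fit looks like.** With events of 1, 1, 1 and 0 in cells of 28, 29, 29 and 28, an ordinary logistic fit did not converge (interaction −22.9, standard error about 93,500). With one event in each cell, the fewest that allow a fit, the standard error is √(4 + 2/27 + 2/28) = 2.04. The 95% interval then spans a factor of exp(1.96 × 2.04), about 55, each way. Even two events per cell, eight in all, give √(4/2 + 2/26 + 2/27) = 1.47 and a factor of about 18.

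**Sensitivity to the rate.** At a 50:50 split, the chance of at least one empty cell is 65% at a 5% event rate, 32% at 8% and 18% at 10%.

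**The other binary component.** For UDPB class 2 or higher, 57 × (0.243 + 0.405) = 36.9 events are expected. All four cells contain an event in 99.9% of trials at 50:50, 96% at 20:80 and 75% at 10:90. The ordinary model generally works, except possibly in small subgroups.

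**The component with no subgroup method.** Treating the components as independent and UDPB as yes/no, two subjects tie on fatal bleeding with probability 0.97² + 0.03² = 0.942, and on UDPB with 0.243 × 0.405 + 0.757 × 0.595 = 0.549. So 0.942 × 0.549, about 52% of pairs, are decided by CTD.

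**A win ratio by drug.** Under the same assumptions, simulation at 28 per arm gave a median win ratio of about 2.9 and an SD of the log win ratio of about 0.37. The difference between drugs on the log scale has a standard error of √2 × 0.37 = 0.52, so the 95% interval for the ratio of win ratios spans exp(1.96 × 0.52), about 2.8, each way.

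**The case against.** The strongest reply has four parts.

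First, a reader might infer that the fatal-bleeding model can never be estimated. The documents do not support that. At 3% it is estimable in about 11% of trials for a balanced factor, and Table 3 describes 3.0% as a minimum rate; with a higher observed rate more fits succeed. The fair statement is that it is unlikely to be estimable at the planned rate.

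Second, Section 11.4 says logistic regression without naming the estimator, and defers detail to the SAP, so an exact or penalised version could still be chosen. That is true. But the model and outcome are already fixed, no sparse-data provision is attached, and a penalised fit would return a number with little information behind it.

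Third, a reader might infer that pooling depends on a subgroup result, or that the plan offers nothing by drug. Neither holds. Sections 1.5, 3 and 11.1 justify pooling by mechanism, indications, bleeding risk and bench removal data. Drug removal is tested separately for each drug within the testing hierarchy. DOAC type is the first factor in Section 11.4, and its UDPB interaction is estimable. Nor do the documents rule out a subgroup win ratio: the Synopsis sentence is general. The revision history records that the win ratio by DOAC type was dropped as a secondary endpoint in version 2.0, which does not bar an exploratory display.

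Fourth, a by-drug win ratio would have wide intervals and could not establish agreement. That stands, and it limits what the addition can do. It would still describe the primary result by a randomisation stratum, on the scale of the primary claim.

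**Conclusion.** The point holds as a minor one about exploratory analyses. On the plan's own event rate and sample size, the interaction model for fatal bleeding has no finite maximum-likelihood estimate in roughly nine trials out of ten for a balanced two-level factor, more often for unbalanced or multi-level factors, and is uninformative otherwise. This rests on the 3.0% rate, on maximum likelihood as the default reading of the text and, apart from DOAC type, on assumed subgroup shares. It does not extend to UDPB class 2 or higher, where the planned model is generally workable.

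Separately, Section 11.4 leaves CTD without a subgroup method and specifies no by-drug estimate of the win ratio. No confirmatory claim, stopping rule or sample size depends on these analyses.

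**What to change.** In Section 11.4 or the SAP:

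- Replace the fatal-bleeding interaction model with counts and percentages by arm and subgroup.
- Keep the logistic interaction model for UDPB class 2 or higher, with Firth penalisation only where a cell is sparse, and state the threshold for sparse in advance.
- Name a subgroup method for 24-hour CTD.
- Add an exploratory win ratio with a 95% confidence interval by subgroup, at least by DOAC type, with a contrast between drugs on the log scale. State that it describes consistency and cannot prove it.

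The cost is a few lines of analysis code. It needs no new data, subjects or alpha. The downside is one more exploratory display with wide intervals, which readers may over-interpret unless it is labelled plainly.
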